4.11.2 Dose intensity**Module 1:**

Dose intensity of AZD4573 and acalabrutinib will be addressed by considering relative dose intensity (RDI). RDI is the percentage of the actual dose delivered relative to the intended dose up to treatment discontinuation. RDI will be defined as:

The actual dose administered in mg of AZD4573 will be derived based on the actual volume (mL), planned dose (mg) collected in EDC, and the planned volume presented in Table 5 under “Total dose volume of diluted study drug (mL)”.

However, there was a high heterogeneity in the handling of AZD4573 preparations between the different sites (eg, some sites provided more diluted solutions which result in higher volume administered without an actual increase in dosing). To consider these different scenarios, the following rules for the derivation of actual dose (mg) will be applied:

- If actual volume (mL) < planned volume (mL):
 - actual dose (mg) = actual volume (mL)/planned volume (mL) x planned dose (mg)

- If actual volume (mL) \geq planned volume (mL) and no overdose indicated in eCRF:
 - actual dose (mg) = planned dose (mg)
- If actual volume (mL) \geq planned volume (mL) and overdose indicated in CRF:
 - actual dose (mg) = actual volume (mL)/planned volume (mL) x planned dose (mg)

Table 5: Examples of AZD4573 dose preparations

Dose (mg)	Required volume of study drug (mL)	Required volume of saline (mL)	Total dose volume of diluted study drug (mL)
1.5	1	60	61
3	2	100	102
6	4	250	254
9	6	250	256
12	8	250	258

Source: AZD4573 handling instructions

RDI (%) = $100 \times d/D$, where d is the actual cumulative dose delivered up to the actual last day of dosing, and D is the intended cumulative dose up to the actual last day of dosing; D is the total dose that would be delivered if there were no modification to dose or schedule. Note: When accounting for the calculation of intended cumulative dose 2 days should be added to the date of last dose to reflect the protocol allowed window for dosing.

The calculation of RDI for AZD4573 is illustrated with the following example. Assume a subject receives final dose of AZD4573 on Study Day 85. This subject was therefore 12.1 weeks (85/7) on treatment. The intended number of doses is therefore 13. From the above formula $D = 6 + 9 + (12 \times 11) = 147$ mg. Assume the actual doses received by the subject is 6, 0, 6, 9, 12, 12, 12, 12, 0 and 12. From the above formula, $d = 81$ mg. RDI for the overall treatment period is therefore $100\% \times 81/147 = 55.1\%$. For the RDI in Cycle 1, $d = 6 + 6 + 9 + 12 + 12 = 45$ (Cycle 1 ends after receiving the 5th dose of AZD4573), and $D = 6 + 9 + (12 \times 3) = 51$. The RDI in Cycle 1 is therefore $100\% \times 45/51 = 88.24\%$.

The following summaries will be produced:

- Summary of Interruptions (including duration of interruptions) and reductions of IP
- Summary of RDI
- Summary of intended and actual exposure AZD4573

Module 2:

The RDI will not be calculated and not presented for Module 2 subjects.

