4.11 Safety and Tolerability Evaluation

Module 1:

Safety, tolerability and DLT data will be listed and summarised as defined by the current AZ standards (oncology early phase study outputs).

The Safety analysis set will be used for all safety and tolerability analyses. All listings and tables, other than those to assess DLTs will be based on the Safety Analysis Set. To describe the DLTs during Cycle 1 in Part A, the DLT-evaluable Analysis Set will be used. To describe DLT-like events beyond Cycle 1 all subjects who receive any amount of study treatment after Cycle 1 will be included.

Module 1 Parts A and B include AEs, AESIs, DLTs in Module 1 Part A Cycle 1, DLT-like events outside of the dose-setting evaluation period, laboratory data, vital signs, and ECGs as safety assessments. In Module 1 Part A, the safety assessments, which also include Cycle 1 DLTs for dose setting, are primary endpoints. In Module 1 Part B, the safety assessments are a secondary endpoint. Listings and summary tables and figures of all safety data for Module 1 Part A and Part B will be created as described in this section. In addition, for Module 1 Part A dose setting MTD (if determined) will be reported.

Module 2:

For Module 2 subjects, all safety data will be presented in separate listings and no summary tables will be provided.

The by subject listing will include the identification of the treatment period (Period 1/ Period 2) when the event occurred and/or the safety assessment was performed.

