4.11.1 Exposure and treatment administration

Module 1:

Exposure amounts, durations and dose modifications and interruptions/delays will be summarised for the following periods:

- Overall treatment period
- Cycle 1
- Up to first tumour assessment
- Cycle 2 onwards

Duration of AZD4573 exposure is defined by the last date of actual AZD4573 dosing (ie, a dose > 0 mg was given) plus 6 days (due to the fact that AZD4573 is ordinarily dosed on a weekly schedule) minus the date of first AZD4573 dose (> 0 mg) plus 1.

- For subjects who die whilst on study treatment or if a DCO occurs, duration of exposure (months/weeks) is defined as date of death/DCO (whichever occurs first) minus the date of first treatment plus 1 day.
- Therefore: Duration of exposure of AZD4573 (weeks) = [min (last dose date where dose > 0 mg + 6, date of death, date of DCO) – first dose date + 1]/7.

Actual duration of exposure (weeks) = [duration of exposure (days) – total duration of dose delays (days)]/7. Duration of exposure is calculated as above, and dose delays are defined as any length of time where the subject has not taken any of the planned dose in accordance with the protocol. The actual exposure calculation makes no adjustment for any dose reductions that may have occurred.

Duration of dose delays of AZD4573 will be derived for doses indicated as being delayed on the eCRF for subjects enrolled on CSP v3.0 and later versions. For each individual dose, the duration of dose delay is the number of days the dose was received outside of the original planned dosing schedule. Overall duration of dose delays will be calculated as the sum of all individual dose delays during the study. For example, assume the eCRF indicate that there was a treatment delay (question “Treatment delayed” indicated as “Y” by investigator) then the duration of the individual delay will be [date first dose received after delay – date last dose received before delay – 9]. 9 is being used to account for the 2-day window. For example, if dose is given on days 1 and 15 with the eCRF indicating a delay, the duration of the delay = 15 – 1 – 9 = 5 days.

The number of subjects with dosing delays and total dose delays will be summarised. Dose delays will also be summarised for number of delays with a duration < 7 days and number of delays with a duration \geq 7 days.

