- Duration of acalabrutinib exposure is defined by the last date of actual acalabrutinib dosing (ie, a dose > 0 mg was given) minus the date of first dose (> 0 mg) plus 1.
 - Duration of exposure acalabrutinib (weeks) = [min (last dose date where dose > 0 mg, date of death, date of DCO) – first dose date + 1]/7.
 - Actual duration of acalabrutinib exposure is the sum of duration of exposure – total duration of dosing delays.

Total and actual treatment duration will be summarised by descriptive statistics for each study drug (AZD4573 and acalabrutinib) and dose level/cohort, separately for Cycle 1 (including ramp-up) and for other treatment cycles. In addition, the number and percentage of subjects with at least one dose interruption will be summarised separately for Cycle 1 (including ramp-up) and for other treatment cycles, for each study drug. Exposure swimmer plot(s) will be produced, with a line presented for each subject to display relevant exposure and disposition details.

Dosing deviations for study intervention (s) will be summarized with reasons for deviations for the following categories: reductions and interruptions.

The following additional summaries will also be produced:

- Number of subjects that completed Cycle 1 (ending a week after receiving 12 mg AZD4573 for three times), including number of subjects that did not complete Cycle 1.
- Number of doses received per subject in Cycle 1.
- Total and actual duration of exposure, specific to Cycle 1.
- Number of subjects that initiated Cycle 2.

Module 1 Part A:

- Number of subjects that completed DLT evaluability period (all doses up to 3rd dose at target level), and number of subjects that did not complete DLT evaluability period
- Number of doses received per subject in DLT evaluability period (including subjects that did not complete DLT evaluability period)
- Actual treatment duration in weeks of exposure specific to DLT evaluability period (including subjects that did not complete DLT evaluability period)
- Number of subjects that initiated Post DLT Evaluability Period

Missed or forgotten doses

Missed and forgotten doses will be included in the listings for dosing but will not be included as dose interruptions in summary tables. However, missed doses will be included in the calculation of actual treatment duration.

Module 2:

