4.11.3 Dose limiting toxicities (DLTs)

Module 1:

DLTs contributing to dose setting in Module 1 Part A Cycle 1 will be listed and summarised separately from AEs which meet the DLT definition criteria but are presented after the initial DLT setting assessment period in Module 1 Part A or in Module 1 Part B (DLT like-events).

The DLT criteria are defined in Section 15.3 of the CSP.

The number of Module 1 Part A dose-setting subjects evaluable for determination of DLTs during the DLT-assessment period and the number of subjects with any DLT will be summarised by dose level. For analysis reporting purposes, the DLTs are as approved and documented at the Safety Review Committee meetings. Excel spreadsheet created manually from the SRC meeting minutes and checked independently by another individual will be shared with the “DLT Evaluability =Y/N” information. The MTD will be selected from all tried dose levels that have not been previously declared to be unsafe with a DU decision according to the mTPI-2 algorithm (see CSP Section 15.2). With this constraint, the MTD will be determined as the dose level with the DLT estimate closest to the target toxicity level of 30%. The MTD will be determined by isotonic regression analysis applied to DLT rates observed in the DLT-assessment period during dose exploration using the mTPI-2 method. In the case of dose levels with estimated toxicity of equal distance (tied dose levels) from the target toxicity of 30%, the following approach is used: among all tied dose levels the highest dose level with target toxicity $\leq 30\%$ will be selected, unless all tied dose levels have estimated toxicity $> 30\%$, in which case the lowest dose level will be selected.

For Module 1 Part B subjects in meeting the same criteria for DLT evaluability that were used for Module 1 Part A dose setting, the number and percentage with any DLT-like event reported as an adverse event, will be summarised.

For pooled RP2D-treated Module 1 Part A and Part B subjects that received 3 AZD4573 doses at target level, the number and percentage that experienced at least one DLT-like event reported as an adverse event after receiving any further amount of study treatment will be summarised.

Types of DLTs and DLT-like events and numbers of events per subject will also be summarised.

Module 2:

This section is not applicable to Module 2 subjects.

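### SAP Section 4.11.2 uses two unreconciled denominators for overall and Cycle 1 RDI in one worked example, and its end of Cycle 1 conflicts with Sections 4.11.1 and 4.3.2

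*SAP*

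**What the plan says.** Section 4.11.2 sets RDI = 100 × d/D, where d is the dose delivered. It describes D twice: "D is the intended cumulative dose up to the actual last day of dosing" and "D is the total dose that would be delivered if there were no modification to dose or schedule". It adds that "2 days should be added to the date of last dose to reflect the protocol allowed window for dosing".

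The worked example has a last dose on Day 85 and a list of ten entries: 6, 0, 6, 9, 12, 12, 12, 12, 0 and 12 mg.

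- **Overall:** 13 intended doses, D = 147 mg, d = 81 mg, RDI 55.1%.
- **Cycle 1:** d = 45 mg, D = 51 mg, RDI 88.24%, with the note that "Cycle 1 ends after receiving the 5th dose of AZD4573".

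Two other sections place the end of Cycle 1. Section 4.11.1 plans this summary: "Number of subjects that completed Cycle 1 (ending a week after receiving 12 mg AZD4573 for three times". The example windows in Section 4.3.2 carry Cycle 1 visits through the third 12 mg dose (Days 26 to 32). Section 4.11.1 also requires separate exposure summaries for Cycle 1 and for Cycle 2 onwards.

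**The concern.** The example serves as the programming specification for RDI, and it handles a skipped week in two ways. Overall, the week counts as intended dose and lowers RDI. In Cycle 1 the denominator is the planned total of five doses however long those doses took, so the same week has no effect. No separate rule for RDI within a cycle is given.

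The end of Cycle 1 adds a second inconsistency. On the undisturbed sequence 6, 9, 12, 12, 12 the fifth dose is the third 12 mg dose, so the definitions agree on the last Cycle 1 dose. In the SAP's own example they do not: the fifth dose received is the second at 12 mg. The next 12 mg dose then belongs to Cycle 1 for visits and completion but falls after Cycle 1 for RDI.

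At stake is the meaning of the reported Cycle 1 dose intensity, and its consistency with the other Cycle 1 exposure outputs, for subjects whose ramp-up was delayed or repeated.

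**Working it through.** **Inputs.** The dose list, Day 85 and the planned sequence (6, 9, then 12 mg) come from the example in Section 4.11.2. Weekly spacing comes from Section 4.11.1: "AZD4573 is ordinarily dosed on a weekly schedule".

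**Intended doses by a given day:** k = floor((day − 1)/7) + 1. **Intended dose for k ≥ 2:** D(k) = 6 + 9 + 12 × (k − 2).

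**1. Reproduce the SAP's figures.**
- Overall: Day 85 gives k = 12 + 1 = 13, and D = 6 + 9 + 12 × 11 = 147. The list sums to d = 81. RDI = 81/147 = 55.1%, as stated. Adding the 2-day window (Day 87) still gives k = 13.
- Cycle 1: d = 6 + 6 + 9 + 12 + 12 = 45 and D = 6 + 9 + 12 × 3 = 51. RDI = 45/51 = 88.24%, as stated.

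**2. Apply the elapsed-time rule to Cycle 1.** Take each listed entry as one weekly slot, a zero being a slot with no dose.
- End at the fifth dose received: slot 6, Day 36. D = 6 + 9 + 12 × 4 = 63 and RDI = 45/63 = 71.4%.
- End at the third 12 mg dose: slot 7, Day 43. D = 6 + 9 + 12 × 5 = 75, d = 45 + 12 = 57 and RDI = 57/75 = 76.0%.

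The 2-day window (Days 38 and 45) changes neither slot count.

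**3. Allow for the undated weeks.** Ten weekly entries end on Day 1 + 7 × 9 = 64, but the example ends on Day 85. The difference is 21 days, so three weeks have no listed entry and could lie inside or outside Cycle 1.

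| Undated weeks inside Cycle 1 | End at fifth dose | End at third 12 mg dose |
|---|---|---|
| 0 | 45/63 = 71.4% | 57/75 = 76.0% |
| 1 | 45/75 = 60.0% | 57/87 = 65.5% |
| 2 | 45/87 = 51.7% | 57/99 = 57.6% |
| 3 | 45/99 = 45.5% | 57/111 = 51.4% |

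Every entry is below 88.24%.

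**4. Separate the two causes.** Changing only the denominator moves 88.24% to 71.4% or lower. Changing only the end of Cycle 1 and keeping D = 51 gives 57/51 = 111.8%. The fall therefore comes from elapsed time. The end point only separates the two columns of the table.

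**The case against.** The strongest reply is that nothing is miscalculated. Both published percentages reproduce, and 51 mg can fairly be read as the dose of an unmodified five-dose Cycle 1. The clause about the last day of dosing may have been written for the overall period only. This stands to the extent that the fault is an undeclared change of convention, not an arithmetic error or a proven breach of the definition. It does not remove the problem, because the SAP gives no per-cycle rule and the two halves of one example treat the same skipped week differently.

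Four stronger readings are tempting, and the document does not support them.

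- **That 71% to 76% is the correct Cycle 1 figure.** It is only the upper end, because the example does not date its doses.
- **That the overall 55.1% is wrong because ten entries do not fill 13 weeks.** Day 85 is given, the rule then yields 147 mg, and unlisted delays are compatible with it. The example lacks dates; its overall result is not shown to be false.
- **That Cycle 1 RDI influences dose selection.** Section 4.11.3 takes the MTD from DLT rates, and Section 4.5 shows that the RP2D had already been declared at a safety review meeting. RDI is descriptive, and delays are also visible in the overall RDI and in the delay and exposure summaries of Section 4.11.1.
- **That percentages of DLT-like events are diluted by subjects no longer treated.** Section 4.11.3 describes a pool of "subjects that received 3 AZD4573 doses at target level" without stating the percentage base. For events beyond Cycle 1, however, Section 4.11 already says that "all subjects who receive any amount of study treatment after Cycle 1 will be included". That largely settles the point.

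**Conclusion.** The point holds as an inconsistency of specification. Section 4.11.2 uses an elapsed-time denominator overall and a fixed 51 mg for Cycle 1 without saying so. Its end of Cycle 1 also differs from Sections 4.11.1 and 4.3.2 in the very example given.

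For the example subject, the stated 88.24% becomes at most 71.4% or 76.0% under the elapsed-time rule, with a floor of about 45%. Mixing the conventions gives 111.8%.

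These figures rest on three assumptions: weekly slots, each listed entry (zeros included) occupying one slot, and the last-day rule applying within a cycle. The effect is confined to a descriptive tolerability output and to subjects with a disturbed ramp-up. No primary endpoint and no dose decision depends on it. It should be corrected because the text as written can produce conflicting Cycle 1 outputs.

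**What to change.** 1. Reconcile the end of Cycle 1 across Sections 4.3.2, 4.11.1 and 4.11.2 with the CSP. State it once, in terms of each cohort's designated target dose level instead of a fixed 12 mg, and refer to that statement elsewhere.
2. Compute the Cycle 1 D by the same elapsed-time rule as the overall RDI: intended doses up to the subject's last Cycle 1 dosing day.
3. Give dates for the doses in the example so that they agree with Day 85, and recalculate both percentages from them.

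The cost is SAP wording and the reprogramming of one derivation. Cycle 1 RDI will be lower for subjects with delays. It would be higher for early stoppers than if a fixed 51 mg were applied to them: a subject who stops on schedule after 6 and 9 mg scores 15/15 = 100% by elapsed time, against 15/51 = 29.4%. Cycle 1 RDI should therefore be read beside the Cycle 1 completion count. The changes concern the analysis derivation only; which clinical definition of Cycle 1 applies is for the sponsor to settle against the CSP.

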4.11.3 Dose limiting toxicities (DLTs)

Module 1:

DLTs contributing to dose setting in Module 1 Part A Cycle 1 will be listed and summarised separately from AEs which meet the DLT definition criteria but are presented after the initial DLT setting assessment period in Module 1 Part A or in Module 1 Part B (DLT like-events).

The DLT criteria are defined in Section 15.3 of the CSP.

The number of Module 1 Part A dose-setting subjects evaluable for determination of DLTs during the DLT-assessment period and the number of subjects with any DLT will be summarised by dose level. For analysis reporting purposes, the DLTs are as approved and documented at the Safety Review Committee meetings. Excel spreadsheet created manually from the SRC meeting minutes and checked independently by another individual will be shared with the “DLT Evaluability =Y/N” information. The MTD will be selected from all tried dose levels that have not been previously declared to be unsafe with a DU decision according to the mTPI-2 algorithm (see CSP Section 15.2). With this constraint, the MTD will be determined as the dose level with the DLT estimate closest to the target toxicity level of 30%. The MTD will be determined by isotonic regression analysis applied to DLT rates observed in the DLT-assessment period during dose exploration using the mTPI-2 method. In the case of dose levels with estimated toxicity of equal distance (tied dose levels) from the target toxicity of 30%, the following approach is used: among all tied dose levels the highest dose level with target toxicity $\leq 30\%$ will be selected, unless all tied dose levels have estimated toxicity $> 30\%$, in which case the lowest dose level will be selected.

For Module 1 Part B subjects in meeting the same criteria for DLT evaluability that were used for Module 1 Part A dose setting, the number and percentage with any DLT-like event reported as an adverse event, will be summarised.

For pooled RP2D-treated Module 1 Part A and Part B subjects that received 3 AZD4573 doses at target level, the number and percentage that experienced at least one DLT-like event reported as an adverse event after receiving any further amount of study treatment will be summarised.

Types of DLTs and DLT-like events and numbers of events per subject will also be summarised.

Module 2:

This section is not applicable to Module 2 subjects.

4.11.4 Adverse Events

Adverse Events (AEs) will be coded using the Medical Dictionary for Regulatory Activities (MedDRA) Version 24.1 or higher and will be graded according to the National Cancer Institute of Common Terminology Criteria for AEs (CTCAE version 5.0).

AEs are defined as treatment emergent (TEAEs) if they onset or worsen (by investigator report of a change in intensity/severity), during the treatment emergent phase defined below. Worsening is determined by comparison with the pre-treatment severity of the AE recorded closest to the start of dosing.

When assigning AEs to the relevant phase of the study the following rules will apply:

- Pre-treatment phase – All AEs with a start date after signing the informed consent form (ICF), prior to the first administration of IP that do not subsequently go on to worsen during the treatment emergent phase.
- Treatment emergent phase – All AEs starting or worsening (severity) following the first administration of IP for the duration of the treatment period, up to and including 30 days after the last dose of study treatment as per the study safety follow-up period but prior to subsequent cancer therapy. AEs with a missing start time which occur on the same day as first IP administration are reported as treatment emergent. Note that the treatment emergent phase includes the on treatment and safety follow-up periods.
- Off-treatment phase – All AEs starting more than 30 days after last dose of study treatment or once subsequent cancer therapy is started, whichever is earlier.

Serious AEs (SAEs)

A SAE is any AE that:

- Results in death
- Is immediately life-threatening
- Requires inpatient hospitalization or prolongation of existing hospitalization
- Results in persistent or significant disability/incapacity
- Is a congenital anomaly/birth defect in offspring of the subject
- Is an important medical event that may jeopardize the subject.

AEs of Special Interest (AESIs)

The following are considered to be AESIs for AZD4573:

- Tumour lysis syndrome (TLS) (see [Section 4.11.12](#))
- Hepatotoxicity (including Potential Hy's Law (PHL), Drug-induced liver injury (DILI), and Bilirubin increase with transaminase increase (ALT or AST or both)).
- Neutropenia (including Febrile neutropenia, Neutropenic sepsis, and Neutrophil count decrease)
- Thrombocytopenia, including Platelet count decrease
- Myocardial ischaemia
- Pyrexia

The following are AESIs for acalabrutinib:

- Ventricular arrhythmias (eg, ventricular extrasystoles, ventricular tachycardia, ventricular arrhythmia, ventricular fibrillation).

Other significant adverse events (OAE)

The list of AESI is comprehensive and no OAEs are not defined.

